7.2. Data and Safety Monitoring Board

An independent Data and Safety Monitoring board (DSMB), composed of an epidemiologist, a pediatrician and a schistosomiasis expert, will be established for the purpose of providing independent advice on the quality of the data produced and the efficacy and safety of the treatment tested, so contributing to safeguarding the interests of the trial participants. The DSMB will also be provided with each SAE report, and with regular statistical reports on frequency and pattern of (S)AEs before the following AM administration.

In this respect, the DSMB will have the possibility to monitor the safety of the treatment on a continuous basis and advise to stop the study if any major safety concern appears.

A DSMB charter, where the relevant terms of reference are clearly defined, will be signed by each member of the DSMB prior to the start of the trial.

8. STATISTICAL METHODS

The statistical analysis will be described in the statistical analysis plan (SAP), written by the biostatistician, which is binding and will be finalized before database lock or before any other analysis takes place.

8.1. Study hypotheses

The primary hypothesis of this study is that one course of AM is non-inferior in terms of efficacy to the standard PZQ treatment. The secondary hypothesis is that repeated courses of AM are superior in terms of efficacy to the standard PQZ treatment. Furthermore, we hypothesize that novel DNA- and antigen-based diagnostics are more accurate than conventional microscopy in assessing the actual antischistosomal treatment response.

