4.3. Sample size

The sample size was calculated on the parasitological cure rate endpoint after the first course of AM, to test the hypothesis that AM is non-inferior to PZQ: at least a 65% cure rate with AM as compared to a 75% cure rate with PZQ according to the following rationale. We consider that a cure rate (CR) of 65% is clinically acceptable as threshold for non-inferiority for the AM combination, for the following reasons: a cure rate above 65% would be very satisfactory compared to all alternative drugs evaluated so far against schistosomiasis, and an efficacy slightly lower than that of PZQ would be largely compensated by the positive clinical effect due to concomitant malaria suppression. Note that this is likely to be marginal in North Senegal where malaria transmission is low, but this "dual" effect could be a major added-value in many other co-endemic regions with higher malaria transmission

Sample size was calculated by simulation to obtain 80% power. The required sample size is 300 schoolchildren per arm. To account for a 20% loss to follow up, the total number of children to be recruited will be 726 (363 per arm). With the same sample size, superiority of repeated courses of AM to PZQ (cure rate of at least 85% after 3 courses) can also be demonstrated with a similar power (i.e. secondary endpoint).

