8.2. Variables of interest

Primary

The primary variables to evaluate are:

- The parasitological cure rates (proportion of subjects negative for both *Schistosoma* species assessed by microscopy over total number in each arm) for AM and PZQ at week 4 after inclusion.
- The patient counts with drug-related adverse events and serious adverse events up to 4 weeks after AM and PZQ administration.

Secondary:

The secondary variables to evaluate are:

- The proportion of cured subjects (CR) of the two different arms at week 10, 16, 24 and 48 (see flowchart).
- The count of patients reporting any form of adverse event up to 4 weeks after each study drug administration.
- The egg reduction rate (ERR) at weeks 4, 10, 16, 24 and 48 (see flowchart). The ERR will be expressed as the percentage of eggs present in each subject at each time point over the number of eggs at baseline.
- The cure rate and egg reduction rate at weeks 4, 10 and 16 after first treatment administration by *Schistosoma* species and by intensity of infection.
- The result of the classic and novel diagnostic tests at baseline and at different time points, as well as a-composite reference standards.
- Clinical and laboratory characteristics related to schistosomiasis-related morbidity at baseline and at weeks 4, 10, 16, 24 and 48
- Prevalence of malaria infection at baseline and at weeks 24 and 48
- The incidence of clinical malaria during the study until week 48
- Counts of cases of anemia both pooled and by severity levels at baseline, week 24 and week
 48
- Binary variables indicating the existence of any or specific types of resistance in the sample size and among the incident malaria cases

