8.3. Statistical methods

8.3.1. Analysis populations

For the efficacy analysis, both an intention-to-treat (ITT) and a per-protocol (PP) approach will be adopted, with the per-protocol analysis being the primary approach, as recommended for non-inferiority studies.

In the PP analysis we will include only subjects who attend all treatment administration visits and that are assessed for infections 4 weeks following every treatment administration. In the ITT population we will include subjects who do not complete all AM administration doses either entirely (missed doses) or inside the pre-specified time window.

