8.3.4. Secondary and tertiary analysis

Secondary analyses

The efficacy of the two treatments over time will be assessed both by calculating the two-sided 95% CI for the difference in proportions of cured subjects at different time points as well as using a mixed effects logistic regression model. Schistosomiasis infection at specific time points will be used as the outcome and treatment and visit as independent variables with a random intercept. Subsequent analyses of the cure rate per *Schistosoma* species and by *Schistosoma* infection intensity will be analyzed in a similar way including those characteristics as covariates in the model. The analyses for

ERR will be done using a linear mixed effects model with a random intercept and a logit link function separately for each *Schistosoma species*. All comparison of proportions will be done using the Chi-square or Fisher's exact test and comparison of continuous characteristics will be done using the Wilcoxon rank sum test. The sensitivity of a specific diagnostic test will be calculated as the proportion of children with schistosomiasis (based on the reference standard used) who have a positive result. The specificity of a diagnostic test will be calculated as the proportion of children without schistosomiasis who have a negative result. The positive predictive value of a diagnostic test will be calculated as the proportion of children with schistosomiasis with a positive result. The negative predictive value of a diagnostic test will be calculated as the proportion of people with a negative result who do not have schistosomiasis. These different values of both novel and classic diagnostic tests will be calculated together with 95% confidence intervals. Composite reference standards will be created by the investigators of the study and will be used as a comparison. An alternative reference standard will be calculated using latent class analysis methodology. The prevalence and patterns of resistant mutations between the two treatment groups will be compared using Chi-square or Fisher's exact test.

Safety analyses

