8.3.6 Multiplicity and Missing Data

An interim analysis is planned at week 16 for the efficacy endpoints of cure rate and egg reduction rate after PZQ administration and single and repeated courses of AM. The endpoints of interest will be analyzed and communicated as soon as the data is collected and cleaned. The analysis and results will not influence follow-up or analysis of the rest of the objectives and endpoints in any way.

The primary analysis is a comparison of a single measurement, thus no adjustments for multiplicity are needed.

Subjects who do not attend all treatment administration visits or the follow-up visits will be considered as missing and will be excluded from the per-protocol analysis. No imputation of missing data will be performed.

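### The superiority comparison for repeated AM takes over a per-protocol primary set justified only for non-inferiority, and its deciding time point is not formally fixed

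*Protocol*

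**What the plan says.** The superiority claim appears in the synopsis, in section 1.2 and in section 8.1: "The secondary hypothesis is that repeated courses of AM are superior in terms of efficacy to the standard PQZ treatment". Section 4.3 gives it a target and a power: "superiority of repeated courses of AM to PZQ (cure rate of at least 85% after 3 courses) can also be demonstrated with a similar power".

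- **Analysis set.** Section 8.3.1 plans both ITT and PP for efficacy, "with the per-protocol analysis being the primary approach, as recommended for non-inferiority studies". PP keeps only children who attended every treatment visit and were assessed four weeks after each treatment administration. Children with missed or late AM doses belong to ITT.
- **Time points.** Section 8.2 lists as a secondary variable "The proportion of cured subjects (CR) of the two different arms at week 10, 16, 24 and 48", without ranking the visits.
- **Method.** Section 8.3.4 says "The efficacy of the two treatments over time will be assessed both by calculating the two-sided 95% CI for the difference in proportions" at the different time points, and also by a mixed-effects logistic model with treatment, visit and a random intercept. Neither is named as deciding.
- **Multiplicity.** Section 8.3.6 says "The primary analysis is a comparison of a single measurement, thus no adjustments for multiplicity are needed". It does not mention the superiority hypothesis. The same section plans an analysis of cure rate and egg reduction rate (ERR) at week 16.

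**The concern.** PP is often preferred for non-inferiority because including children who deviated from treatment can make two arms look alike. For superiority that argument falls away, and what matters is comparing the groups as randomised. Here the PP filter is also unequal. The AM arm has three courses and many more occasions to miss a dose, vomit a repeat dose or be withdrawn for intolerance (sections 4.5 and 6.1), and each can remove a child from PP. The AM children who remain are a more selected group than the PZQ children beside them.

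The unnamed time point is a second, smaller problem. The trial is open label, and the week-16 results are to be communicated before weeks 24 and 48 are complete. If the deciding visit is not fixed beforehand, it could be chosen with part of the answer known. The week-4 non-inferiority conclusion does not depend on either problem. At stake is the trial's other powered claim.

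**Working it through.** **1. What PP requires in each arm** (visit schedule in section 5.1, PP rule in section 8.3.1)

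| | AM | PZQ |
|---|---|---|
| Dosing days to attend | 3 courses × 3 days = 9 | 1 |
| Assessments four weeks after treatment | weeks 4, 10, 16 = 3 | week 4 = 1 |
| Total conditions | 12 | 2 |

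A PZQ child needs a week-16 sample to contribute to a week-16 analysis, but the PP rule does not select on it. The documents give no attendance or tolerance rates by arm, so the size and direction of the resulting bias cannot be calculated.

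**2. The protocol's own sample size**

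Inputs from section 4.3: "at least a 65% cure rate with AM as compared to a 75% cure rate with PZQ", "Sample size was calculated by simulation to obtain 80% power", and 300 per arm. The margin of 10 points and the two-sided 95% CI come from section 8.3.3. With a true cure rate of 75% in both arms:

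n = (1.96 + 0.8416)² × 2 × 0.75 × 0.25 / 0.10² = 7.849 × 0.375 / 0.01 ≈ 295 per arm.

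The stated 300 is reproduced closely. Simulation with the Wilson-score interval at 300 per arm gives 81.1% power.

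**3. Power for one superiority test, 85% v 75%, two-sided 5%**

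At 300 per arm, the standard error under the null is √(2 × 0.80 × 0.20 / 300) = 0.03266. Under the alternative it is √((0.85 × 0.15 + 0.75 × 0.25) / 300) = 0.03240.

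Power = Φ((0.10 − 1.96 × 0.03266) / 0.03240) = Φ(1.11) = 86.7%.

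If 20% of 363 are lost, 0.8 × 363 ≈ 290 remain, and power is 85.5%. The power statement in section 4.3 therefore holds for a single test.

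**4. Which visits fit the powered claim**

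Courses are given at weeks 0, 6 and 12. Week 10 follows course 2, so it falls outside a target defined after three courses. Weeks 16, 24 and 48 remain. Three places favour week 16:
- section 5.1 titles that visit as the parasitological evaluation after the third AM round, and describes weeks 24 and 48 as clinical efficacy evaluations (microscopy is still repeated there);
- the last assessment that PP requires is at week 16;
- section 8.3.6 schedules the repeated-course efficacy analysis at week 16.

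No sentence designates it.

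**5. Error rate if any of the three visits could carry the claim**

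Each visit is read at one-sided 2.5%, the upper half of a two-sided 95% CI. If independent: 1 − 0.975³ = 7.3%. For correlated visits, equicorrelated normal test statistics were simulated. The correlation is an assumption, since the protocol gives none.

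| Assumed correlation | False-superiority rate | Multiple of 2.5% |
|---|---|---|
| 0 | 7.3% | 2.9 |
| 0.5 | 6.3% | 2.5 |
| 0.9 | 4.2% | 1.7 |

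With one named visit and one test, the rate is 2.5%.

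**The case against.** The strongest reply is that the protocol calls this a secondary hypothesis, and that a hierarchy and a deciding test for secondary endpoints commonly go in the SAP. Section 8 makes the SAP binding and final before any analysis. That stands: the SAP was not available, and the absence of a hierarchy here is not in itself an error. The reply does not reach the analysis set, because the protocol itself makes PP primary for efficacy and gives a reason that does not fit superiority. ITT is also planned, which softens the point, but as the secondary approach.

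Three stronger readings are tempting, and the documents do not support them.

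- **That no analysis set is named.** Section 8.3.1 names two and ranks them. The fault lies in the ranking for this comparison.
- **That a false superiority claim is about three times as likely as stated.** The protocol states no error rate for superiority and has no rule that any one visit suffices. A figure near three (7.8%, or 3.1 times 2.5%) needs four visits including week 10, an any-visit rule and an assumed correlation of 0.5.
- **That the mixed model adds a further claim at each visit.** Section 8.3.4 states no treatment-by-visit interaction, so as written the model gives one overall treatment effect.

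**Conclusion.** The point holds in two parts. The firmer one is that following section 8.3.1 as written makes the main superiority comparison one between unequally selected groups, with 12 attendance conditions in the AM arm against 2 in the PZQ arm. This rests on reading the PP rule literally. The bias cannot be sized from the documents.

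The lesser part is that the deciding visit is not formally fixed, although the text leans to week 16. The false-superiority rate of about 6% depends on three visits, an any-visit rule and an assumed correlation, so it measures what is left open and not what the plan prescribes. The primary week-4 conclusion is unaffected. This should be corrected, but it does not threaten the trial's main result.

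**What to change.** - **Section 8.3.1:** make ITT primary for the superiority comparison with PP as supportive, and keep PP primary for week-4 non-inferiority.
- **Sections 8.1 and 8.3.4:** name the week-16 difference in cure rate, with its two-sided 95% CI, as the deciding contrast. Label the other time points, the mixed model and ERR as supportive.

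This takes a few sentences and needs no added children or data. The downside is that weeks 24 and 48 could no longer carry a superiority claim alone. Testing superiority only after week-4 non-inferiority succeeds is optional: it ties two different regimens together and would make the superiority result descriptive if the first test failed.

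One limit should be acknowledged. Section 8.3.6 rules out imputation, and section 4.5 aims for at least weeks 24 and 48 in withdrawn children. Week-16 outcomes may therefore be missing for some randomised children, and their number should be reported by arm.

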8.2. Variables of interest

Primary

The primary variables to evaluate are:

- The parasitological cure rates (proportion of subjects negative for both *Schistosoma* species assessed by microscopy over total number in each arm) for AM and PZQ at week 4 after inclusion.
- The patient counts with drug-related adverse events and serious adverse events up to 4 weeks after AM and PZQ administration.

Secondary:

The secondary variables to evaluate are:

- The proportion of cured subjects (CR) of the two different arms at week 10, 16, 24 and 48 (see flowchart).
- The count of patients reporting any form of adverse event up to 4 weeks after each study drug administration.
- The egg reduction rate (ERR) at weeks 4, 10, 16, 24 and 48 (see flowchart). The ERR will be expressed as the percentage of eggs present in each subject at each time point over the number of eggs at baseline.
- The cure rate and egg reduction rate at weeks 4, 10 and 16 after first treatment administration by *Schistosoma* species and by intensity of infection.
- The result of the classic and novel diagnostic tests at baseline and at different time points, as well as a-composite reference standards.
- Clinical and laboratory characteristics related to schistosomiasis-related morbidity at baseline and at weeks 4, 10, 16, 24 and 48
- Prevalence of malaria infection at baseline and at weeks 24 and 48
- The incidence of clinical malaria during the study until week 48
- Counts of cases of anemia both pooled and by severity levels at baseline, week 24 and week
 48
- Binary variables indicating the existence of any or specific types of resistance in the sample size and among the incident malaria cases

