The analyses for ERR will be done using a linear mixed effects model with a random intercept and a logit link function. The diagnostic accuracy of both novel and classic diagnostic tests will be calculated together with 95% confidence intervals. The prevalence and patterns of resistant mutations between the two treatment groups will be compared using Chi-square or Fisher's exact test.Safety analyses The number of subjects experiencing a SAE, up to 4 weeks after PZQ and AM administration will be compared between treatment groups using Fisher's exact test.		(CI) for the difference in proportions as well as using a mixed							
model with a random intercept and a logit link function.The diagnostic accuracy of both novel and classic diagnostictests will be calculated together with 95% confidenceintervals. The prevalence and patterns of resistant mutationsbetween the two treatment groups will be compared usingChi-square or Fisher's exact test.Safety analysesThe number of subjects experiencing a SAE, up to 4 weeks afterPZQ and AM administration will be compared betweentreatment groups using Fisher's exact test.		effects logistic regression model.							
The diagnostic accuracy of both novel and classic diagnostic tests will be calculated together with 95% confidence intervals. The prevalence and patterns of resistant mutations between the two treatment groups will be compared using Chi-square or Fisher's exact test. Safety analyses The number of subjects experiencing a SAE, up to 4 weeks after PZQ and AM administration will be compared between treatment groups using Fisher's exact test. Safety will be		,							
The diagnostic accuracy of both novel and classic diagnostic tests will be calculated together with 95% confidence intervals. The prevalence and patterns of resistant mutations between the two treatment groups will be compared using Chi-square or Fisher's exact test. Safety analyses The number of subjects experiencing a SAE, up to 4 weeks after PZQ and AM administration will be compared between treatment groups using Fisher's exact test. Safety will be		model with a random intercept and a logit link function.							

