infection rapidly spread throughout the northern region. A decade later, this severe *S. mansoni* epidemic was followed by a shift towards *S. haematobium* infection, which also reached record prevalences. Today, schistosomiasis is still highly endemic in Senegal, despite national control efforts. Both *S. mansoni* and *S. haematobium* are wide-spread, resulting in a large number of people with mixed infections in the communities ⁷.

Since the 1970s, treatment schistosomiasis has relied almost exclusively on praziquantel (PZQ). PZQ has demonstrated good efficacy ¹ in a meta-analysis of 55 comparative and non-comparative trials involving > 19,000 participants, of whom 68% were school-age children ⁸; results can be summarized as follows:

- For *Sh* infection, the WHO-recommended 40 mg/kg single dose of PZQ achieved a cure rate (CR) of 77.1% (95% confidence interval [CI] 68.4-85.1%; 2,645 participants/20 studies) and a mean egg reduction rate (ERR) of 94.1% (1,957 participants/19 studies).
- For *Sm* infection, the WHO-recommended 40 mg/kg single dose of PZQ achieved a CR of 76.7% (95% CI 71.9-81.2%; 6,377 participants/45 studies) and a mean ERR of 86.3% (5,546 participants/39 studies).
- For mixed Sh/Sm infection, CR was 63.5% (95% CI 48.2-77.0%; 379 participants/6 studies).

Another meta-analysis comparing school-age and preschool-age children in 47 comparative/noncomparative studies showed similar efficacy results in both age groups ⁹. The WHO has set a tentative ERR threshold of 90% as an indicator of optimal efficacy ¹⁰. In a systematic review of 10 studies, CR and ERR of *Sm* infection increased with repeated PZQ administrations, but such an effect was not observed for *Sh* ¹¹.

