Thanks to its safety, efficacy and low cost, PZQ has become the mainstay of schistosomiasis control. It is the drug of choice for mass drug administration (MDA) programs targeting high risk groups, including school-age children. PZQ is administered at regular intervals with the aim of reducing parasite load and preventing severe disease (the so-called 'preventive chemotherapy')^{1,12}. Recommended time intervals between MDAs depends on the level of endemicity, but most of time PZQ is distributed annually to children 6 to 12 years of age, through school-based interventions. In 2015, PZQ has been distributed to 66.5 million of the estimated 218.8 million people requiring preventive chemotherapy worldwide, with a coverage of 42.2% in school-age children ¹³. This is supposed to further increase in the coming years to reach the target 75% coverage in this age group and to extend treatment to pre-school children ^{9,14}.

Despite the progress in schistosomiasis control attributed to preventive chemotherapy with PZQ, alternative therapeutics are urgently needed. The main reasons are 15,16 :

- PZQ is efficacious against all *Schistosoma* species, but only against the adult worms. Its activity against immature schistosome larvae is extremely weak, in the first few days up to 6-7 weeks after infection, before increasing progressively thereafter ^{17,18}. Treatment failures have usually been attributed to high reinfection rates by non-susceptible immature larvae, especially in high transmission areas, where large-scale and long-term use of PZQ monotherapy through repeated MDA in school-age children has not resulted in satisfactory community control so far ¹⁹.
- The extensive use of PZQ in monotherapy may result in the emergence of drug resistance ²⁰. PZQ resistance can be induced experimentally ^{21,22} and there have been sporadic reports on

¹ Efficacy is usually measured by the cure rate (CR: the proportion of egg-positive individuals, as assessed by urine and stool microscopy, who become egg-negative after treatment) and egg reduction rate (ERR: reduction of the post-treatment arithmetic and/or geometric mean egg count compared to pre-treatment mean count).

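### ERR is defined as each child's percentage of eggs remaining, contrary to the protocol's own definition as a reduction, and its linear model with a logit link contradicts itself

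*Protocol*

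**What the plan says.** The protocol defines ERR twice.

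- **Background (section 1.1.1, footnote 1):** "ERR: reduction of the post-treatment arithmetic and/or geometric mean egg count compared to pre-treatment mean count". This is a reduction, computed on group means. The main text of the same section adds: "The WHO has set a tentative ERR threshold of 90% as an indicator of optimal efficacy". It cites mean ERRs for PZQ of 94.1% (*S. haematobium*) and 86.3% (*S. mansoni*).
- **Variables of interest (section 8.2):** "ERR will be expressed as the percentage of eggs present in each subject at each time point over the number of eggs at baseline". This applies at weeks 4, 10, 16, 24 and 48.

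The model is fixed in section 8.3.4: "ERR will be done using a linear mixed effects model with a random intercept and a logit link function". The two species are to be modelled apart. The synopsis gives the same model.

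Three other statements bear on the point. Section 8.2 counts as cured the "proportion of subjects negative for both" species. Section 4.2 admits children with eggs in urine, stool or both. Section 8.3.6 plans an analysis of cure rate and ERR at week 16, to be communicated as soon as the data are collected and cleaned.

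**The concern.** The two definitions differ in direction (remaining or reduced) and in level (one ratio per child or a ratio of group means). A reader who sets the trial's ERR beside the 90% benchmark or the cited PZQ figures would be comparing different quantities.

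The model raises a separate problem. A linear mixed model works on the scale of the response, that is, with an identity link. Adding a logit link makes it a different model, and the text does not say which is meant. The choice decides whether egg-free children contribute to the analysis at all. Neither reading suits a ratio that can exceed 100% when counts rise, or one with a zero denominator in the by-species analysis.

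At stake are the ERR figures and the between-arm ERR comparison, including those due at week 16.

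**Working it through.** **Inputs.** 300 evaluable children per arm and a PZQ cure rate of 75% (section 4.3); a cure rate of at least 85% after three AM courses (section 4.3); a margin of 10 points with a two-sided 95% CI (section 8.3.3); the two ERR definitions; the model in section 8.3.4.

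**Plan's own figure.** The protocol gives no planned ERR value to reproduce. The 300 per arm, used here only to count egg-free children, does reproduce. With 75% in both arms, one-sided alpha 0.025 and 80% power, n = (1.960 + 0.842)² × 2 × 0.75 × 0.25 / 0.10² ≈ 295 per arm, within 2% of 300.

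**Direction.** Percentage remaining = 100 − percentage reduced.

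| Quantity | As a reduction | As worded in 8.2 |
|---|---|---|
| Benchmark | 90% | 10% |
| PZQ, *S. haematobium* | 94.1% | 5.9% |
| PZQ, *S. mansoni* | 86.3% | 13.7% |
| Cured child | 100% | 0% |

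**Level.** Take two children, one going from 10 to 20 eggs and one from 400 to 20.
- Group reduction, arithmetic means: 1 − (20 + 20)/(10 + 400) = 1 − 40/410 = 90.2%.
- Mean per-child percentage remaining: (200% + 5%)/2 = 102.5%, whose complement is −2.5%.
- Group reduction, geometric means: 1 − 20/√(10 × 400) = 1 − 20/63.2 = 68.4%.

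Subtracting from 100 therefore repairs the direction but not the level. The third line shows why the type of mean has to be stated; the footnote allows either.

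**Model read as a logit transform.** logit(x) = ln(x/(1 − x)) is not finite at 0 or 1 and does not exist above 1. A cured child has x = 0. At the 75% assumed for PZQ that is 0.75 × 300 = 225 children at week 4; at 85% after three AM courses it is 0.85 × 300 = 255. Taking the complement does not help, because logit(1) is infinite too.

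**Model read as a true link.** A link acts on the mean, so individual zeros are allowed. This was checked on simulated data: 300 children per arm, zeros drawn with probability 75% and 65%, the rest from an assumed beta(1, 4) distribution. Of the 600 values 424 were zero. A logit transform left 176 usable. A fractional-response model with a logit link, without the random intercept, converged on all 600 and returned the observed PZQ mean of 5.6%. However, such a model needs responses between 0 and 100%. A normal-error version with a logit link still forces every expected value below 100%, so it cannot represent a rise in egg count.

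**Can ratios exceed 100%?** The protocol gives no frequency. It does make rises plausible: the area is highly endemic, section 1.1.1 links treatment failure to reinfection, the PZQ arm receives no further study drug until week 48, and ERR is assessed up to week 48.

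**By species.** A child infected with one species only has 0 in the denominator for the other, so the ratio does not exist.

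**The case against.** The case on the other side is substantial, and much of it stands.

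- **A reader might infer that ERR is undefined for every cured child, or that most children cannot enter the model.** The text does not support this. A cured child's ratio is 0%, which is a defined value; only its logit is not finite. Section 8.3.4 speaks of a link, and a true link accepts zeros. Cured children are lost only under the transform reading.
- **A reader might infer that the inversion biases the comparison of arms.** It does not. Since logit(1 − p) = −logit(p), modelling the share remaining instead of the share removed only reverses the sign of the treatment effect.
- **A reader might infer that an effective drug would be failed against the 90% benchmark.** The benchmark stands in the background; section 8 never tests ERR against it. The harm is a misreported figure, not a wrong decision rule.
- **65% is not a planned AM cure rate.** Section 4.3 gives it as the lowest acceptable rate, and the sample size reproduces with 75% in both arms. The count of 225 therefore uses the PZQ assumption alone.
- **Some of this is detail for the SAP.** Handling of zeros, of rises and of children negative for a species could be left there, and a per-child ERR is a legitimate choice if explained. But the protocol itself fixes the inverted definition and the contradictory model. An SAP that follows them inherits the fault, and one that departs from them conflicts with the protocol.

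**Conclusion.** The point holds in a limited form. Section 8.2 defines the complement of an egg reduction, per child, against the protocol's own group-mean definition. A 90% reduction would be reported as 10%, and averages of the per-child ratios cannot be set beside the cited ERRs or the benchmark even after subtraction from 100. The model in section 8.3.4 and the synopsis is incoherent as worded. One reading has no finite value for 225 of 300 children at the assumed PZQ cure rate; the other admits those children but cannot represent rising counts. The by-species ratio is undefined for children without that species at baseline.

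The count of 225 rests on the 75% assumption and on cure meaning no eggs of either species, so such a child scores zero for whichever species was present at baseline. How often counts rise is not known from the document. The SAP was not available and may already address part of this.

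ERR is one of several unranked secondary endpoints. The primary non-inferiority analysis of cure rate does not use it and is unaffected.

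**What to change.** - **Section 8.2:** define ERR = 100 × (1 − mean egg count at the visit / mean egg count at baseline), per arm and per species, among children egg-positive for that species at baseline. State whether the mean is arithmetic or geometric; if geometric, state how zero counts enter. Give a bootstrap 95% CI that resamples children.
- **Section 8.3.4 and synopsis:** replace the linear model with a logit link by one coherent model that admits zeros and increases. One option is a negative binomial mixed model on the egg counts with a log link, with arm, visit and their interaction, a random intercept per child, and an offset for the amount of stool or urine examined. Other models that meet the same two conditions would serve.
- **Timing:** make the change before the week 16 analysis, since ERR is to be reported there.

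The cost is rewording of these sections and matching text in the SAP. No new data, visits or participants are needed.
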